## 1. INTRODUCTION

Treatment of fungal infections remains a significant challenge to clinicians, particularly for patients requiring intensive care unit (ICU) management where the incidence of invasive fungal infections and associated mortality rate are distinctly high[1]. Response to antifungal therapy is generally sub-optimal despite the emergence of extended spectrum novel anti-fungals like the echinocandins and triazoles. Although the relative incidence of invasive fungal infection is low, and hence therapeutic anti-fungal dosing is relatively less frequent, prophylactic use of oral/systemic antifungal agents has become a very common indication due to the increasing use immunosuppressants during critical care, cancer chemotherapy and organ transplantation [2,3]. This has led to a wide systemic exposure to antifungal drugs in considerable number of patients. In parallel, such widespread use increases the risk of emergence of resistant fungi, unless adequate exposure is defined and ensured during clinical use of the drugs. Unfortunately, it has been a challenge to explicitly describe the dose-exposure-response relationships in all target patient populations, especially for new antimicrobials prior to their wide clinical application.

Posaconazole is a new extended spectrum triazole active against a range of yeasts and molds including *Aspergillus*, *Candida*, *Coccidioides*, *Cryptococcus neoformans*, *Fusarium*, and *Zygomycetes*[4]. It may be used for the prevention of invasive fungal infections in immunocompromised patients including febrile neutropenic patients and those receiving immunosuppressant drugs for graft-vs-host disease during stem cell transplantation[5]. It may also be used for treatment of systemic fungal infections [6].The use of posaconazole in ICU patients has been limited to stable patients to ensure reliable bioavailability from the oral formulations [7].Oral formulations have important limitation in that they cannot be used in critically ill patients who may be unable to take oral doses or bioavailability may be compromised due to erratic absorption. Recently, an intravenous (IV) formulation has been developed to address these limitations[8]. Initial pharmacokinetic (PK) investigations of the IV formulation were conducted in hematology patients [8], with further data in other patient populations still forthcoming; particularly in the critically ill where the IV formulation would probably be used most frequently.

Most of the available PK data for posaconazole is from non-critically ill patients who received the oral formulation. Although the absorption phase of the kinetics is not relevant for the IV formulation, data on the distribution, metabolism and elimination properties would still be informative of the IV kinetics. The tissue distribution of posaconazole is extensive with a very large volume of distribution owing to its high lipophilicity[9]. It is highly bound to plasma proteins (98-99%) and therefore very likely to be affected by the variable changes in plasma protein concentration in critically ill patients. The major elimination pathway of posaconazole is through biliary excretion (about 77%) of mainly the

unchanged parent compound and the rest through renal excretion of as a glucuronide conjugate [9,10]. Thus, posaconazole PK is expected to be hardly affected in patients with renal impairment including those undergoing haemodialysis[11,12]. The extent of hepatic metabolism is also limited that the influence of hepatic dysfunction on the PK of posaconazole appears minimal; existing studies have not indicated a need for dosing adjustment in hepatic impairment although monitoring plasma concentration is advocated [10,13]. Other factors such as demographic variables including age, sex and race reportedly have no clinically relevant influence on the PK of posaconazole in healthy adults [14] suggesting no need of dose titration for these covariates.

However, a number of studies have described PK variability due to altered absorption/bioavailability which can frequently result in sub-therapeutic plasma concentrations, forming strong case for therapeutic drug monitoring [15,16]. Nonetheless, it is unclear whether the observed low concentrations can also be explained, at least in part, by other factors such as disease-related PK changes or if the obvious plausibility of altered absorption has masked such investigations. Most population PK models described so far are based on one compartment models, which do not reveal if the observed variability in concentrations is due to changes in PK parameters such as volume of distribution or clearances [17]. The influence of disease state on these PK parameters has been extensively described for several antimicrobials in the critically ill patient populations [18,19]. Although data on the new IV formulation of posaconazole in this patient population is lacking, there is evidence from previous PK studies on the oral formulation that PK variability not observed in healthy study participants was observed in patients with invasive fungal infections, although it was explained primarily in relation to altered bioavailability from the oral formulation[10]. In surgical ICU patients, Störzinger *et al.*[7] observed low plasma concentration of posaconazole, which was administered via nasogastric tube. Similar findings were reported in general ICU patients[20]. Although the explanation in these reports was again the irregular absorption, the influence of other pathologic changes remains to be investigated. A PK evaluation of IV posaconazole in critically ill patients, not confounded by the absorption factor, would reveal if there is any pathophysiology-induced PK alteration. Such a study will also give insight into the dose-exposure relationships and optimal treatment regimen, although the pharmacodynamic (PD, exposure-response relation) of posaconazole is yet to be clarified.

Posaconazole is thought to exhibit both concentration and time dependent antimicrobial activity, which can be described by the ratio of AUC/MIC[21,22]. However, PD studies are limited and inconsistent that the optimal dosing target is yet to be described[17]. Generally maintaining higher concentrations may be necessary to improve patient outcomes[6,15,17,23]. Some guideline recommendations are steady state trough concentrations greater than 0.7 mg/L may be required for prophylaxis and greater than 1mg/L for treatment of invasive fungal infections[3]. Clearly, more data

is required to accurately describe optimal plasma concentration-response relationships as there is inconsistency between studies/authors in the recommended trough concentrations [3,10,15]. However, it is also clear that the clinical efficacy is well correlated with plasma concentration [15]. It is, therefore, essential to describe the relationship between dosing regimens and subsequent exposure through a thorough PK analysis, particularly for the new IV formulations, which pharmacokinetically may behave differently from the oral formulations that have been investigated so far. Such PK analysis would provide the foundation for the design of optimal dosing regimens for ICU patients, through PK/PD based modelling and clinical trial simulations. The application of population PK models also extends to the determination of susceptibility breakpoints through analysis of dosing simulations data [24]. This would be invaluable given the limited clinical experience of posaconazole in the ICU settings and that, previous break points which correspond to the oral dosing regimens [24,25], may not be relevant to the applications of the IV formulation in ICU patients.

This prospective, observational, pharmacokinetic study of posaconazole aims to describe the population PK of posaconazole after a single IV dose administration in the critically ill. It will assess the influence of pathophysiologic changes including altered plasma protein concentrations/binding in the critically ill on the PK of posaconazole.

## **2. CLINICAL HYPOTHESES**

[figure not shown]
- Pharmacokinetic properties of the new intravenous posaconazole formulation will be distinct as compared to the previous oral formulations
- Dose-exposure relationships from the new formulation may be different in intensive care unit patients as compared to general wards patients, due to disease-related factors
- Changes in plasma protein concentration or binding capacity in the critically ill may affect the pharmacokinetics of posaconazole

## **3. OBJECTIVES**

- To describe the pharmacokinetics of intravenous posaconazole in critically ill patients
- To assess the influence of critical illness on the pharmacokinetics of posaconazole administered via intravenous infusion
- To assess the impact of altered plasma protein concentrations/binding in the critically ill on the pharmacokinetics of posaconazole

## 4. STUDY DESIGN

This is a prospective, observational, pharmacokinetic study. The study will enrol eight patients with presumed or confirmed systemic fungal infections, who are admitted to ICU. Patients aged greater than 18 years with established central venous access for drug administration and no history of allergy for triazole antifungals will be approached for enrolment if they have not taken posaconazole within two weeks of time and if they are not pregnant. A single dose of 300mg IV posaconazole will be administered to eight study participants. Serial blood samples will be collected at pre-defined time points for determination of both total and unbound plasma concentrations. Structured data collection sheets will be used to collect other clinical data. The data generated will be subject to population pharmacokinetic analysis using computer software. Monte Carlo simulations will be performed to describe dose-exposure relationships.

**Figure 1. Study flow chart**

## **5. STUDY PROCEDURES**

### **5.1 Patient screening**

All patients admitted to the ICU at the Royal Brisbane and Women's Hospital (RBWH) during the study period with suspected or confirmed fungal infections and receiving/requiring systemic antifungal therapy will be screened for eligibility to participate in this study based on the under listed inclusion and exclusion criteria.

#### **Inclusion criteria**

- Age  $\geq$  18 years
- Admission for ICU care
- The presence of suspected or confirmed fungal infection requiring systemic antifungal therapy
- Presence of central venous access for drug administration

#### **Exclusion criteria**

- Age  $<$  18 years
- Pregnancy
- Prescription of drugs that are known to interact with posaconazole
- Oral posaconazole use within the last two week prior to enrolment
- Documented history of drug reaction to the triazole antifungal medications

A decision to prescribe an anti-fungal therapy will occur as part of the routine care by the attending clinicians. After such a decision has been made by the doctors treating the patient, the study will use the opportunity of this clinical condition that requires treatment with systemic anti-fungal medications, to investigate the pharmacokinetics of the study anti-fungal medication (a new intravenous formulation of posaconazole). Therefore, this study does not aim to initiate treatment for a suspected or proven systemic fungal infection for the study purpose, and will recruit patients only after such a decision is made by the doctors treating the patients.

The usual circumstances for the diagnosis of a suspected systemic fungal infection that requires treatment with systemic anti-fungal medications are non-specific and involve empiric assessment of the patient's clinical condition, assessment of potential risk factors as well as clinical interpretation of various diagnostic mycological and radiological investigations. Proven systemic fungal infections are those confirmed by presence of hyphae in a histological or cytological specimen with further evidence of tissue damaged seen in histological examinations, or positive culture for a clinical specimen with a clinical or radiological sign of infection at the site from which specimen was taken. Serologic tests

(mainly for *Aspergillus*, *Blastomyces*, *Candida*, *Coccidioides*, *Cryptococcus*, and *Histoplasma*) are also used to confirm fungal infections. The diagnosis of either a suspected or confirmed systemic fungal infection by the doctors treating the patient warrants treatment with systemic anti-fungal medications.

## **5.2 Patient enrolment**

Patients that meet all the inclusion criteria and none of the exclusion criteria will be approached for informed consent. Investigators of the study will explain the procedures of the study verbally in addition to the structured patient information sheet that will be provided for the participants prior to consenting. The participants' next of kin will be approached if any of the participants are not in a position to give consent due to medical sedation or unconsciousness or severe illness. A total of 8 patients will be enrolled.

## **5.3 Drug administration**

All patients enrolled in the study will receive the usual treatment with anti-fungal agent(s) as per the standards of practice at the study hospital. The usual care for suspected or confirmed systemic fungal infections will be at the discretion of the clinical team treating the patient and in accordance with the local guidelines and standards of practice. The typical initial empiric therapy for suspected or proven invasive fungal infections in patients at the Royal Brisbane and Women's Hospital is fluconazole. Voriconazole or amphotericin B may also be considered as an alternative initial agent in immunocompromised patients if invasive aspergillosis is confirmed or if there is a high suspicion of a mould infection. In non-neutropenic patients with invasive candidiasis, fluconazole may be used if the organism is deemed susceptible. For fluconazole-resistant candidiasis in non-neutropenic patients, caspofungin is the agent most likely to be used. For suspected or proven acute invasive aspergillosis, voriconazole is first-line therapy although amphotericin B or caspofungin may also be used.

In addition to the drugs given as part of the usual care as described above, a single dose of posaconazole will be administered for the study purpose. A single dose of 300 mg intravenous posaconazole solution, diluted with 0.9% sodium chloride or 5% dextrose in water, will be administered to each study participant by slow infusion over 90 minutes through a central venous access. The drug will be infused through a 0.22 micron polyethersulfone (PES) or polyvinylidene difluoride (PVDF) filter. The magnitude of the single dose chosen for this study is in accordance with with the approved maintenance dosing regimen.

## 5.4 Sample collections

Serial blood samples will be collected just before and after administration of the single dose of posaconazole. The first sample will be collected immediately before commencing of the posaconazole infusion. The next three samples will be collected during drug infusion at 15 min, 45min and 75 minutes after commencing the infusion. The fifth sample will be taken at the end of line flushing (15-20min) after the 90 minutes infusion. The next samples will be taken at 3h, 5h, 8h, 12h, 18h, 24h, 30h, 36h and 48h after the commencement of drug infusion. The actual time of collection for individual samples will be recorded and used for analysis. Lithium heparin tubes will be used for sample collection. The volume of each blood samples will be 2-3ml. The plasma will be separated by centrifugation (3000 rpm for 10 minutes) and frozen under - 80°C for storage until the subsequent assay of total and unbound posaconazole concentration.

## 5.5 Clinical data collection

Patients' electronic and paper based medical records will be reviewed to collect clinical data including demographic characteristics, list of diagnosis, microbiological data, vital signs, and clinical haematological and chemistry data. A structured data collection sheet will be used to collect these patient specific clinical data, which will include the following:

- Physical examination including vital signs
- ICU and Hospital admission and discharge dates and times
- Acute Physiology and Chronic Health Evaluation II [APACHE II] score and risk of death at ICU admission, APACHE II diagnosis upon recruitment
- Sequential Organ Failure Assessment [SOFA] score at ICU admission and daily during ICU antibiotic course
- Presence of shock on days of sampling
- Presence of mechanical ventilation
- Serum creatinine concentrations
- Urinary creatinine clearance (if available)
- Hepatic function markers (alanine aminotransferase (ALT), aspartate aminotransferase (AST), alanine phosphatase ALP), gamma glutamyl transferase (GGT), international normalised ratio (INR), bilirubin
- Medication list on days of sampling
- Antimicrobial Data: type, dose, dosing interval, duration of infusion
- RRT data:
  - Filter type, filter size, filter age at time of sampling

- Blood flow rates
- Dialysate dose
- Haematocrit
- Pre/post dilution dose
- Patient fluid balance on day of sampling and targeted hourly fluid removal
- Changes made to settings during sampling interval
- Transmembrane pressure
- Infection data:
  - Organisms isolated and sample type,
  - Minimum inhibitory concentration if available

All case report forms and other data (including without limitation, written, printed, graphic, video and audio material, and information contained in any computer database or computer readable form) created or developed in connection with the Study will be owned by the Principal Investigator. All data will be collected by study research staff.

## **5.6 Sample assay**

An LC-MS/MS method for determination of total and unbound posaconazole concentrations in human plasma will be developed, validated and used for analysis of patient samples. Previously, we have successfully developed and utilized LC-MSMS methods for the determination of unbound drug concentration using plasma protein ultrafiltration technique for sample preparation. A similar approach will be employed to develop a method for determination of unbound posaconazole concentration. Our bio-analytical laboratory has state-of-the-arts technology with highly qualified analytical chemists who have developed and validated assay methods for various antimicrobials. Therefore, it is highly likely that a validated method will be available at our laboratory when the study progresses and samples are available for analysis. However, if the need arises, samples can be analysed at Pathology Queensland, Royal Brisbane and Women's Hospital, where a validated LC-MS/MS method for posaconazole assay exists.

## **6. PHARMACOKINETIC ANALYSIS**

Pharmacokinetic data analysis will be performed on both the total concentration and unbound plasma posaconazole concentration following the procedures described below.

### **6.1 Initial non-compartmental analysis**

The plasma concentration-time data will be subject to non-compartmental pharmacokinetic analysis using computer software applications such as PK-Solver or WinNonlin. The linear trapezoidal rule

will be followed for computation of area under the concentration-time curve. Results will be summarized for preliminary description of the single dose PK parameters, which will be utilized as initial estimates in the subsequent population PK analysis.

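### Section 6.1 uses the linear trapezoidal rule throughout, which slightly overstates AUC on the decline after the infusion, and more so when samples are missed; linear-up/log-down is a cheap improvement but only a partial remedy

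*Combined protocol and SAP*

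**What the plan says.** Section 6.1 plans a non-compartmental analysis "using computer software applications such as PK-Solver or WinNonlin". For AUC it states "The linear trapezoidal rule", which "will be followed for computation of area under the concentration-time curve. Results will be summarized for preliminary description of the single dose PK parameters". No different rule is given for falling concentrations. The results serve as a preliminary description of single-dose parameters, "which will be utilized as initial estimates in the subsequent population PK analysis". Section 6 applies the analysis to both total and unbound concentrations.

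Section 5.3 gives "A single dose of 300 mg intravenous posaconazole solution", delivered "by slow infusion over 90 minutes through a central venous access". Section 5.4 schedules 14 samples: one before the dose; three during the infusion at 15, 45 and 75 minutes; one after a 15-20 minute line flush (about 1.75 to 1.83 h from the start); and nine more: "The next samples will be taken at 3h, 5h, 8h, 12h, 18h, 24h, 30h, 36h and 48h after the commencement of drug infusion". Actual sampling times are used.

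The plan has no rule for missed samples and no rule for extrapolating AUC beyond 48 h, and it does not list which NCA parameters will be reported.

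**The concern.** Nine of the 14 samples lie on the decline, and the gaps between them widen from 2 h to 12 h. On a convex, roughly exponential decline the chord between two samples lies above the curve, so the linear rule errs upwards. The error grows with the length of the interval relative to the half-life. It is therefore larger in patients who eliminate the drug faster and in patients with missed samples, and it need not cancel across patients. With eight patients, one or two incomplete profiles can move a summary.

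At stake is the accuracy of the NCA description of single-dose exposure, and of clearance if that is derived from it. Linear-up/log-down is a standard alternative that is usually less biased here and needs no extra data.

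**Working it through.** The plan states no AUC, clearance or half-life, so there is no figure of its own to reproduce. The check takes dose, infusion time and sampling times from sections 5.3 and 5.4 and assumes the pharmacokinetic parameters.

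**Step 1: one interval.** For mono-exponential decline at rate k over an interval Δt, put x = kΔt. The ratio of linear area to true area is x(1 + e^−x) / [2(1 − e^−x)].

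| Interval, in half-lives | Overstatement by the linear rule |
|---|---|
| 0.25 | 0.25% |
| 0.5 | 1.0% |
| 1 | 4.0% |
| 2 | 15.5% |

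The log rule is exact on such an interval.

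**Step 2: whole profiles, no assay noise.** Exact profiles for 300 mg over 1.5 h were evaluated at 0, 0.25, 0.75, 1.25, 1.8, 3, 5, 8, 12, 18, 24, 30, 36 and 48 h. Each rule's AUC0-48 was compared with the exact integral. There were eight assumed cases: three one-compartment (half-life 6, 12 and 27 h) and five two-compartment (CL 7-20 L/h, V1 30-100 L, Q 30-100 L/h, V2 150-250 L; terminal half-life about 10-32 h). Bias in AUC0-48:

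| Samples missed | Cases | Linear | Linear-up/log-down |
|---|---|---|---|
| None | all eight | +0.12% to +1.96% | −0.31% to +0.15% |
| 24, 30, 36 h | all eight | +1.9% to +12.0% | at most 0.31% in size |
| 3, 5 h | two-compartment | +4.1% to +27.3% | +3.2% to +14.6% |
| 3, 5, 8 h | two-compartment | +7.3% to +52.9% | +5.8% to +28.6% |

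Share of bias removed = 1 − |log-down bias| / |linear bias|.

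- Full schedule: 68-96% in six of the eight cases and 34% in a seventh. In the eighth the net bias moves from +0.12% to −0.21%.
- Late samples lost: 89-99% in the two-compartment cases and 96-98% in the one-compartment cases.
- 3 and 5 h both lost, two-compartment: 20-46%. For example, 1 − 14.63/27.26 = 46%. The log rule assumes one exponential within the interval, and here there are two.
- 3 h alone lost, in the fastest-clearing case: +9.46% against +3.89%, so 1 − 3.89/9.46 = 59%.

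NCA clearance is dose/AUC to infinity. With the tail extrapolated from the last three points (an assumption), the linear rule biases it by −0.1% to −1.9% on the full schedule.

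**Step 3: the interval across the end of infusion.** The samples at 1.25 h and about 1.8 h straddle the unsampled peak at 1.5 h. In all five two-compartment cases the later value is below the earlier one. The linear rule nevertheless understates that interval by 6.6-11.1%, and the log rule by 6.6-12.8%.

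**Step 4: varied patients.** 4000 simulated patients had CL 7 L/h, V1 80 L, Q 40 L/h and V2 170 L, each with about 40% variability. With all samples, mean AUC0-48 bias was +0.7% (5th to 95th percentile +0.3% to +1.3%) for linear and +0.15% for log-down. With 20% of the 3-36 h samples lost at random, separate runs gave a mean of +2.2% to +2.3% (95th percentile about +7%) for linear and +1.0% to +1.1% (about +4%) for log-down.

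**The case against.** The strongest objection is that nothing the study concludes depends on this. Section 6.1 is headed as an initial analysis. The covariate work and dosing simulations in section 6.2 rest on NONMEM fits to the concentrations themselves, where no trapezoids enter, and a starting value that is 1% off should not change a converged fit. The full-schedule bias is also small beside sampling error. With the assumed 40% variability the log-scale SD is √ln(1 + 0.4²) = 0.385, so the standard error of a geometric mean with n = 8 is 0.385/√8 = 0.136, about 14%. A bias of 0.7% is about one-twentieth of that. With an assumed 10% assay error, per-patient root mean square error is 3.3% for linear and 3.1% for log-down. All of this stands, and it makes the point minor.

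The missed-sample figures are hypothetical: the documents give no missing rate, and section 11 describes one-to-one nursing around the clock. That also stands. It limits how much weight those figures can carry, but 48 hours of serial sampling in intensive care makes some gaps plausible.

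The objection does not remove the point. The plan says the NCA values will be summarised, and the alternative rule is less biased in most of the assumed conditions at almost no cost.

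**Conclusion.** The point holds as a minor improvement. The linear rule overstates AUC, and understates any clearance derived from it, on the convex decline after the infusion ends. The net bias in AUC0-48 is about +0.1% to +2% with the full schedule. With an assumed 20% random loss it averages about +2%, with a 95th percentile of about +7%. All sizes rest on assumed parameters.

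A reader might infer three stronger things that are not supported:

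- **That every falling interval is overstated.** The interval across the end of infusion is understated, and neither rule corrects it.
- **That log-down cures the bias at no cost.** It removes only about 20-46% when the 3 and 5 h samples are both lost from a two-compartment profile, and it is undefined at zero. Values below quantification are plausible for the unbound drug, because section 1 puts protein binding at 98-99%.
- **That the population estimates or simulations are biased.** Section 6.2 fits concentrations directly, so only the preliminary summary and the starting values are touched.

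**What to change.** In section 6.1, replace the sentence on the AUC rule with:

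*AUC will be computed by the linear-up/log-down trapezoidal rule (linear while concentrations rise, logarithmic while they fall), reverting to the linear rule for any interval with a zero or below-quantification value.*

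Actual sampling times, and use of both total and unbound data, are already covered in sections 5.4 and 6 and need not be repeated. The cost is one sentence and a changed calculation rule, with no extra samples or data. The small downside is the fallback, which will matter mainly for unbound concentrations.

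The same edit could usefully say how missed samples and extrapolation beyond 48 h are handled. In the assumed cases with a half-life of 27-32 h, 30-33% of AUC to infinity lies beyond the last sample, so extrapolation may matter more for NCA clearance than the choice of trapezoidal rule.
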